1.6 Compliance Statement

This study will be conducted in full accordance of all applicable Children’s Hospital of Philadelphia Research Policies and Procedures and all applicable Federal and state laws and regulations including 45 CFR 46. All episodes of noncompliance will be documented.

The investigators will perform the study in accordance with this protocol, will obtain consent, and will report unanticipated problems involving risks to subjects or others in accordance with The Children’s Hospital of Philadelphia IRB Policies and Procedures and all federal requirements. Collection, recording, and reporting of data will be accurate and will ensure the privacy, health, and welfare of research subjects during and after the study.

2 STUDY OBJECTIVES

2.1 Primary Aims

2.1.1. Our first primary aim is to compare fat and energy absorption from the diet in subjects with CP and healthy subjects utilizing the MBT, CFA and BC methods to characterize fat and energy absorption patterns.

2.1.2. Our second primary aim is to determine if, in subjects with CP, fat and energy absorption will improve after pancreatic enzyme medication utilizing the MBT, CFA and BC methods to characterize the fat and energy absorption patterns.

2.2 Secondary Aims

2.2.1. The **secondary aim** of this proposal is to utilize these data to optimize the MBT design and application by reducing the time and blood samples required.

2.2.2. We will also **explore** the utility of the MBT compared to the CFA and BC (both require the burdensome 72-hour total stool and dietary intake collection) in identifying differences in fat absorption between subjects with CP and healthy individuals and within the CP cohort, with and without pancreatic enzyme medication.

3 INVESTIGATIONAL PLAN

3.1 General Schema of Study Design

3.1.1 Screening Phase

Potential subjects will be screened using the protocol inclusion and exclusion criteria. Subjects will be recruited from regional academic hospitals and gastroenterology, and pancreatology subspecialty centers. Primary recruitment centers will include: 1) University of Pennsylvania Medical Center Hospital; 2) Pennsylvania Hospital; 3) Presbyterian Hospital; and 4) Philadelphia Veterans Administration Medical Center. Other likely collaborators and recruitment centers may include: 1) GI Centers at the Jefferson Medical Center; 2) Main Line Medical Center (Lankenau and Bryn Mawr Hospitals); and 3) other regional centers. These outside institutions will be involved with recruitment of subjects only and will otherwise not be engaged in the research. We will recruit the healthy subjects from the greater Philadelphia region using general adult practices, flyers, and recommendations from subjects with CP regarding healthy family and friends interested in participating. The CHOP Recruitment Enhancement Core (REC) will be utilized to recruit healthy adult subjects. The Recruitment Enhancement Core provides assistance with recruitment plan development and may assist in identifying and contacting potential participants using the Clinical Recruiting Unit (CRU), the CHOP Recruitment Registry and internal communication resources. Our research team anticipates no difficulty in enrolling well-qualified participants with the proposed sample size and staff (see **Table 2. Study Timeline**). Informed consent will be obtained prior to any study related procedures being performed, and this will include the discontinuation of pancreatic enzyme medication for those participants who are taking this medication at the time of enrollment in the study.

3.1.2 Study Treatment Phase

All study visits will occur at outpatient research offices of the Clinical and Translational Research Center at The Children's Hospital of Philadelphia (CHOP), a pediatric health care center. Eligible subjects will be enrolled into the study and come to CHOP for the study visits. Refer to Table 1 for list of assessments and the study timeline for the pace of recruitment.

3.1.3 Open-label treatment with Creon36™

Subjects with CP only will receive Creon36™ intervention and return to CHOP for Visit 2, about one to two weeks after their Visit 1. Refer to Table 1 for list of assessments and the study timeline for the visit schedule.

3.2 Allocation to Treatment Groups and Blinding

This is an open-label intervention therapeutic exploratory study, and not a randomized controlled trial.

3.3 Study Duration, Enrollment and Number of Sites

3.3.1 Duration of Study Participation

The study duration per subject will be up to four weeks for the subjects with CP. The study duration for healthy subjects will be up to one week.

3.3.2 Total Number of Study Sites/Total Number of Subjects Projected

The study will be conducted at one investigative site in the United States, the Children's Hospital of Philadelphia. Recruitment will occur across regional centers as described above.

Recruitment will stop when 24 subjects with CP and 24 healthy comparison subjects are enrolled. It is expected that 24 subjects in each group will be enrolled to produce 22 evaluable subjects in each group.

3.4 Study Population

3.4.1 Inclusion Criteria

Chronic Pancreatitis Cohort

- Chronic pancreatitis diagnosis by gastroenterologist. Participants with CP will be characterized based on the TIGAR-O (toxic, genetic, autoimmune, recurrent, obstructive) etiology system, on pancreatic morphology (Cambridge criteria) when available, and on physiological state (exocrine and endocrine function) as recommended by the recent American Pancreatic Association Practice Guidelines⁴.
- Age 30-75 years old
- Evidence of at-risk for malabsorption including: 1) history of use of and response to pancreatic enzyme medication; 2) history of unintentional weight loss; 3) history of increased stools per week or fatty stools; and/or 4) other clinical signs or symptoms suggestive of fat malabsorption
- In usual state of health for past two weeks including no change in medications

-
- Able to consume a moderate fat diet for stool evaluations
 - Able to participate in the study for about four weeks with two study visits

Healthy Cohort

- Age 30-70 years old
- No known chronic disease that would affect dietary intake or fat absorption
- In usual state of health for past two weeks, with stable medications, diet and weight
- BMI from 14-35
- Able to consume a moderate fat diet for stool evaluations
- Able to participate in the study for about one week with one study visit

3.4.2 Exclusion Criteria**Chronic Pancreatitis Cohort**

- Evidence of normal fat absorption in medical record
- Medications that alter fat absorption (i.e. orlistat, other weight loss medications, ursodeoxycholic acid)
- Allergy to pork products
- History of intestinal blockage or fibrosing colonopathy
- Current diagnosis of gout and treatment with allopurinol medical therapy
- Pregnancy or breast feeding

Healthy Cohort

- Evidence of fat malabsorption
- Medications that alter fat absorption (i.e. orlistat, other weight loss medications, ursodeoxycholic acid)
- Pregnancy or breast feeding

4 STUDY PROCEDURES**4.1 Screening**

Subjects will be screened with support from the clinical sites using the protocol inclusion and exclusion criteria. Clinic staff will inform eligible individuals of the existence of this study and ask for permission from these individuals to share their contact information with the CHOP study staff. Either verbal or in person screening can occur. In the instance of screening over the phone, verbal subject permission will be obtained. In the instance of in person screening, study staff will obtain a signature from the subject. For both instances, screening consent will occur prior to obtaining any information from study subjects.

All subjects will be enrolled in their usual state of good health defined as no hospitalizations, emergency room or unscheduled acute illness clinic visits, and with activity levels and food intake considered typical by the subject for two weeks prior to Visit 1.

Healthy subjects will be identified from the greater Philadelphia region using referrals of friends and family of the subjects with CP. The subjects with CP will first ask for potential healthy subjects'

permission to release their contact information to the CHOP study team. Healthy subjects will also be identified using general adult practices, CHOP staff interested in participating in a research study, and through the CHOP Recruitment Enhancement Core (REC). The Recruitment Enhancement Core provides assistance with recruitment plan development and may assist in identifying and contacting potential participants using the Clinical Recruiting Unit (CRU), the CHOP Recruitment Registry and internal communication resources. Verbal subject permission will be obtained prior to obtaining any health information from these subjects to determine eligibility.

4.2 Study Treatment Phase

Subjects with CP will have two visits in this study. Visit 1 will be without pancreatic enzyme medication and Visit 2 will occur after they receive Creon36™ as their pancreatic enzyme medication therapy. Healthy subjects will have one visit only in this study. Both Visit 1 and 2 are identical with the exception of the several questionnaires (home environment, health history, quality of life) and fecal elastase assessment which are only collected once (refer to study procedures in Table 1). Collection of the saliva sample for genetic testing will only occur once, during Visit 1.

Visit for Consent and HIPAA Authorization for release of medical record information

- Informed Consent will be obtained at a visit to precede Day 1 of protocol before any study procedures take place. If subjects are taking pancreatic enzyme medication and will need to discontinue medication 3 days prior to Visit 1, the visit for informed consent will occur prior to the beginning of any discontinuation of the medication. HIPAA Authorization forms from the subjects' institutions will be obtained and will be signed in person or obtained by mail/fax/email.
- Instructions in preparation for study procedures will be given in person at this consent visit.

There are two protocols for Visit 1. The first protocol is for subjects with CP who are naïve to pancreatic enzyme medication, that is, they have not received pancreatic enzyme medication prior to Visit 1. The second protocol for Visit 1 is for subjects with CP who are currently taking pancreatic enzyme medication and will require a pancreatic enzyme medication washout period, that is, they will not take pancreatic enzyme medication for three days prior to Visit 1 (a "pancreatic enzyme medication washout" period). Subjects with CP will be prescribed Creon36™ as their pancreatic enzyme medication therapy and will receive this therapy for Visit 2. Visit 2 will be the same for all subjects with CP.

Healthy subjects will have Visit 1 only.

Visit 1: Protocol for All Healthy Subjects and for Subjects with CP who have not Received Pancreatic Enzyme Medication Prior to Visit 1

Day 1

- Regular lunch/dinner except for no intake of dairy products
- No alcohol intake
- Normal daily activity

-
- Fast overnight starting at 8 pm
-

Day 2 – CHOP Visit to CTRC Outpatient Lab and NGL

- Urine pregnancy test for pre-menopausal females
 - Insert heplock catheter
 - Baseline blood draw for MBT, Fat soluble vitamins (A, D, E, K), pre-albumin, serum zinc and selenium (Both Cohorts).
 - Baseline blood draw for CMP, CBC and fatty acid panel (CP Cohort only)
 - Saliva collection for DNA sequencing (CP Cohort only)
 - Administer MBT study meal (breakfast)
 - MBT – hourly blood sample for 8 hours
 - After hour 6 a low fat study lunch
 - Anthropometry (height, weight, skinfolds, circumferences)
 - Whole body DXA (CP cohort only)
 - Spot stool sample will be collected for Fecal Elastase I (CP Cohort only)
 - Questionnaires: Home Environment (Visit 1), Health History and medications, Quality of life questionnaire (MOS SF-36), PROMIS, Adherence, Adverse Events (Visit 2)
 - Instructions will be given for collection and shipping for: stool collection (72-hour fecal fat analysis and bomb calorimetry), 3-day weighed food records, and adverse events diary
 - Prescribe Creon36™ and dispense to subjects with CP (CP Cohort only)
-

Day 3 - Home

- Maintain adverse events diary
-

Day 4 - Home

- Moderate fat diet
 - 3-day weighed food record begins
 - Food record – Day 1
 - Maintain adverse events diary
-

Day 5 - Home

- Moderate fat diet
 - Food record – Day 2
 - Stool collection begins (72-hour fecal fat and bomb calorimetry), store frozen until brought to CHOP.
 - 72-hour stool – Day 1
 - Maintain adverse events diary
-

Day 6 - Home

-
- Moderate fat diet
 - Food record – Day 3
 - 72-hour stool – Day 2
 - Maintain adverse events diary
-

Day 7 - Home

- Moderate fat diet
- 72-hour stool – Day 3
- Maintain adverse events diary

Visit 1: Protocol for Subjects with CP who are Receiving Pancreatic Enzyme Medication Prior to Visit 1 and require a Washout Period

Participants discontinuing pancreatic enzyme medication will be without this medication for the nine days encompassing Visit 1.

Days 1 & 2

- Discontinue pancreatic enzyme medication (Washout)
-

Day 3

- Discontinue pancreatic enzyme medication (Washout)
 - Regular lunch/dinner except for no dairy intake
 - No alcohol intake
 - Normal daily activity
 - Fast overnight starting at 8pm
-

Day 4 – CHOP Visit to CTRC Outpatient Lab and NGL

- Urine pregnancy test for pre-menopausal females
- Insert heplock catheter
- Baseline blood draw for MBT, Fat soluble vitamins (A, D, E, K), pre-albumin, serum zinc and selenium (both cohorts)
- Baseline blood draw for CMP, CBC, and fatty acid panel (CP Cohort only)
- Saliva collection for DNA sequencing (CP Cohort only)
- Administer MBT study meal (breakfast)
- MBT – hourly blood sample for 8 hours
- After hour 6 a low fat study lunch
- Anthropometry (height, weight, skinfolds, circumferences)
- Whole body DXA (CP Cohort only)
- Spot stool sample will be collected for Fecal Elastase I (CP Cohort only)

-
- Questionnaires: Home Environment (Visit 1), Health History and medications, Quality of life questionnaire (MOS SF-36), PROMIS Survey, Adherence, Adverse Events (Visit 2)
 - Instructions will be given for collection and shipping for: stool collection (72-hour fecal fat analysis and bomb calorimetry), 3-day weighed food records, and adverse events diary
 - Prescribe Creon36™ and dispense to subjects with CP (CP Cohort only)
-

Day 5 - Home

- Maintain adverse events diary
-

Day 6 - Home

- Moderate fat diet
 - 3-day weighed food record begins
 - Food record – Day 1
 - Maintain adverse events diary
-

Day 7 - Home

- Moderate fat diet
 - Food record – Day 2
 - Stool collection begins (72-hour and bomb calorimetry), store frozen until brought to CHOP.
 - 72-hour stool – Day 1
 - Maintain adverse events diary
-

Day 8 - Home

- Moderate fat diet
 - Food record – Day 3
 - 72-hour stool – Day 2
 - Maintain adverse events diary
-

Day 9 - Home

- Moderate fat diet
 - 72-hour stool – Day 3
 - Maintain adverse events diary
-

4.3 Open-Label Treatment with Creon36™

Subjects with CP only will receive open-label treatment with Creon36™ as their pancreatic enzyme medication therapy and will receive this therapy for nine days encompassing Visit 2. Visit 2 will be the same for all subjects with CP.

Visit 2: Pancreatic Enzyme Medication Treatment Protocol for Subjects with CP Only

Days 1 & 2

- Pancreatic enzyme medication treatment (two Creon36™ with meals, and one Creon36™ with snacks)

Day 3

- Pancreatic enzyme medication treatment (two Creon36™ with meals, and one Creon36™ with snacks)
- Regular lunch/dinner except for no dairy intake
- No alcohol intake
- Normal daily activity
- Fast overnight starting at 8pm

Day 4 – CHOP Visit to CTRC Outpatient Lab and NGL

- Pancreatic enzyme medication treatment (two Creon36™ with meals, and one Creon36™ with snacks)
- Insert hepllock catheter
- Baseline blood draw for MBT, Fat soluble vitamins (A, D, E, K), pre-albumin, serum zinc and selenium, CMP, CBC and fatty acid panel
- Saliva sample for genetic testing
- Administer MBT study meal (breakfast)
- MBT – hourly blood sample for 8 hours
- After hour 6 a low fat study lunch
- Anthropometry (height, weight, skinfolds, circumferences)
- Adherence to pancreatic enzyme medication and Adverse Events Questionnaires
- Instructions will be given for collection and shipping for: stool collection (72-hour fecal fat analysis and bomb calorimetry), 3-day weighed food records, and adverse events diary

Day 5 - Home

- Pancreatic enzyme medication treatment (two Creon36™ with meals, and one Creon36™ with snacks)

-
- Resume usual diet
 - Maintain adverse events diary
-

Day 6 - Home

- Pancreatic enzyme medication treatment (two Creon36™ with meals, and one Creon36™ with snacks)
 - 3-day weighed food records begins
 - Food record – Day 1
 - Maintain adverse events diary
-

Day 7 - Home

- Pancreatic enzyme medication treatment (two Creon36™ with meals, and one Creon36™ with snacks)
 - Food record – Day 2
 - Stool collection (72-hour and bomb calorimetry), store frozen until brought to CHOP.
 - 72-hour stool – Day 1
 - Maintain adverse events diary
-

Day 8 - Home

- Pancreatic enzyme medication treatment (two Creon36™ with meals, and one Creon36™ with snacks)
 - Food record – Day 3
 - 72-hour stool – Day 2
 - Maintain adverse events diary
-

Day 9 - Home

- Pancreatic enzyme medication treatment (two Creon36™ with meals, and one Creon36™ with snacks)
 - 72-hour stool – Day 3
 - maintain adverse events diary
-

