Patients with CP are rarely evaluated for RPF/PI because there are no non-invasive, clinically available, affordable, acceptable and reliable diagnostic tests. Historically, the CFA is considered the gold standard for RPF/PI diagnosis. However, CFA is almost never used in clinical care in large part due to patient burden related to 72-hr stool and diet collections. The CFA method requires the patient consume a moderate fat diet, accurately document all food intake and collect all stool for 72-hours. A dietitian analyzes the record using software that calculates the daily and three day average fat intake (g/day). The multiple stool sample containers are shipped to one of a few laboratories that homogenizes and measures stool fat content (g/day). CFA% is calculated by the clinician once both diet and stool results are available. Lastly, reference ranges for healthy individuals evaluated with modern techniques for stool and dietary collections, and fat extraction and measurement are unavailable.

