5.2 Efficacy

5.2.2. Diagnostic tests, Scales, Measures

Malabsorption Blood Test (MBT): The **MBT primary outcomes** consist of parameters from pharmacokinetic analyses. The MBT consists of a simultaneous oral dose of pentadecanoic acid (PA), a free fatty acid, and triheptadecanoic acid (THA), a triglyceride with three heptadecanoic (HA) saturated fatty acids requiring hydrolysis by pancreatic lipase before HA can be intestinally absorbed (Patent # US 7402405 B2, July 22, 2008). The MBT with the PA and THA is delivered in a breakfast test meal after a 12-hour fast and 24 hours without dairy foods. Serum concentration

levels of PA and HA are assessed by gas-liquid chromatography (GC), from serum samples drawn prior to MBT and then hourly for eight hours. The MBT test meal is prepared immediately before consumption, with 5.0g of PA and 5.5g of THA blended into a test meal composed of 64g vanilla Scandishake (Axcan Scandipharm, Birmingham, AL), 6oz silk light chocolate soy milk, and 10ml microlipids (www.nestle-nutrition.com). The 8oz MBT test meal contains ~550 calories, 32 g fat, and 52% of calories from fat. The test meal was designed to be similar to a high fat dinner meal. Prior to administration of the MBT test meal, an indwelling catheter is placed for baseline (0 Hour) and subsequent blood draws at Hour 1, 2, 3, 4, 5, 6, 7 and 8 post ingestion for quantification of serum PA and HA. The MBT test meal is consumed within five minutes of the baseline blood draw. After the Hour 6 blood draw, subjects consume a 1000 kcal, low fat (12 g) lunch meal, and two blood samples will follow this meal (Hours 7 and 8). During the eight-hour protocol period, subjects are offered non-caloric and non-caffeinated beverages *ad libitum*. The 72-hour home stool collection will begin two days after the MBT visit, and the corresponding 3-day weighed food record will begin the day prior to the first day of the 72-hour stool collection.

Table 3. Protocol for each MBT visit

Protocol	Day 1	Day 2	Day 3	Day 4	Day 5	Day 6	Day 7	Day 8	Day 9
Enzyme-naïve: MBT #1 CP Healthy Comparisons	- Fast from 8pm - No dairy - No alcohol - Normal activity	- MBT at 8am - Lunch at 2pm - 9 hourly blood draws	Home Return to usual diet	- Diet record (day 1)	- Diet record (day 2) - 72-hour stool (day 1)	- Diet record (day 3) - 72-hour stool (day 2)	- 72-hour stool (day 3)		

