Coefficient of Fat Absorption (CFA): The **CFA primary outcome**, the coefficient of fat absorption (CFA%) will be determined by the 72-hour stool collections at Visits 1 and 2 and a 3-day weighed food record collection while consuming a moderate fat (about 80+ g/day) diet. These stool collections will be performed at home and returned to CHOP. Subjects will be given a home collection kit and detailed instructions. Specimens will be stored frozen until analysis of total fat content by a gravimetric method (Mayo Medical Laboratories, Rochester, MN). Total dietary intake of fat during the 3-day period will be assessed from the 3-day weighed food records which will coincide with the 72-hour stool collection, and the CFA% will be calculated⁶⁷. The CFA% will be compared 1) between the CP cohort and the healthy reference group, and 2) with pancreatic enzyme medication exposure compared with pancreatic enzyme medication-naïve status in the CP cohort.

Bomb calorimetry (BC): The BC primary outcome for BC is the assessment of energy loss in the stool from the 72-hr stool collection (NIDDK sponsored research unit, Phoenix Indian Medical Center, Phoenix, AZ) using bomb calorimetry⁶⁸⁻⁷⁰. Samples will be shipped frozen and the heat of combustion (energy) will be measured in a bomb calorimeter, with energy liberated quantified in kcal/g stool. The energy loss from the stool will be compared 1) between the CP cohort and the

healthy comparison group, and 2) with pancreatic enzyme medication exposure compared with pancreatic enzyme medication -naive status in the CP cohort.

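### The protocol contradicts itself on the diet and the visit interval for the two 72-hour stool collections, so off-enzyme and on-enzyme stool may not be collected under like conditions

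*Combined protocol and SAP*

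**What the plan says.** **Diet.** Section 4.2 has two Visit 1 day lists. Each puts "Moderate fat diet" on every food-record and stool day: Days 4–7 for healthy and enzyme-naive subjects, Days 6–9 for the washout group. The Visit 2 list in Section 4.3 covers the same activities on Days 6–9. Its Day 6 entry reads "3-day weighed food records begins", and no diet line appears from there to Day 9. The last diet instruction, on Day 5, sends subjects back to their usual diet. Section 5.2.2 bases CFA% on "72-hour stool collections at Visits 1 and 2 and a 3-day weighed food record collection while consuming a moderate fat (about 80+ g/day) diet". Section 4.2 also says "Both Visit 1 and 2 are identical with the exception of the several questionnaires" and the fecal elastase test; diet is not among the exceptions.

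**Interval.** The Synopsis (Study Phases) counts one to four weeks from the close of the Visit 1 stool collection. Section 3.1.3 counts roughly one to two weeks from Visit 1 itself. Section 1.4 starts Creon36 three days before Visit 2. Section 4.2 states "Visit 1 will be without pancreatic enzyme medication".

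**First stool day.** The MBT text in Section 5.2.2 says "The 72-hour home stool collection will begin two days after the MBT visit". The day lists and Table 3 start it three days after.

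**Duration.** Section 3.3.1 caps CP participation at four weeks; the Synopsis gives four weeks as approximate.

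**The concern.** H2 compares the same CP subjects off and on Creon36 with no control arm, so anything else that differs between the two collections is counted as drug effect.

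If the Visit 2 list is followed as printed, diet may differ. This bears mainly on bomb calorimetry, where "The energy loss from the stool will be compared" between conditions and no division by intake is stated. CFA% is partly protected, since "CFA% is calculated by the clinician once both diet and stool results are available" and the calculation divides by recorded fat intake. The MBT is done before the home diet days.

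If Visit 2 is booked at the short end of the Section 3.1.3 window, some stool labelled off-enzyme is produced on Creon36. That stool serves H1 (CP against healthy) as well as H2, and the overlap pulls both towards no difference.

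**Working it through.** **1. The plan's own figures (Section 6.4).** Paired t-test, n = 22, two-sided 0.05, noncentrality (difference/SD) × √22 on 21 df. CFA%: 9/14 = 0.643. Stool energy: 36/56 = 0.643. Power is 82.0% for each, consistent with the stated 80%. The sample size is not in dispute.

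**2. Visit windows, in days after Visit 1.** Visit 1 is Day 2 (naive) or Day 4 (washout). Stool days are 5–7 or 7–9, so +3 to +5 in both.
- Synopsis: 5 + 7 = +12 to 5 + 28 = +33.
- Section 3.1.3: +7 to +14.
- Common to both: +12 to +14.

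**3. Overlap of Creon36 with the off-enzyme stool days.** Creon36 starts at Visit 2 minus 3.

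| Visit 2 | Creon36 starts | Overlap, stool +3 to +5 | Overlap, stool +2 to +4 (Section 5.2.2 text) |
|---|---|---|---|
| +7 | +4 | 2 days | 1 day |
| +8 | +5 | 1 day | 0 |
| +9 or later | +6 or later | 0 | 0 |

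Visits at +7 or +8 also conflict with Sections 5.2.2 and 9.4.2, which keep washout subjects off enzyme through +5.

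**4. Duration.** At the Synopsis upper limit the last stool day is 7 + 28 + 5 = Day 40 (naive) or 9 + 28 + 5 = Day 42 (washout). A 28-day cap allows Visit 2 no later than 28 − 5 − 2 = +21 or 28 − 5 − 4 = +19.

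**5. Cost of overlap (upper bound).** Assume each overlapped day takes the full planned effect (CFA 85% off, 94% on). One day in three moves the off-enzyme mean by 9/3 = 3 points, so the mean change is 9 − 3 × days × fraction of subjects affected (SD 14, n = 22).

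| Fraction overlapping | One day: change, power | Two days: change, power |
|---|---|---|
| None | 9, 82% | 9, 82% |
| Quarter | 8.25, 75% | 7.5, 67% |
| Half | 7.5, 67% | 6, 48% |
| All | 6, 48% | 3, 16% |

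Allowing for the extra variance from mixing subjects changes these by at most 2 percentage points. Stool energy gives the same powers, because its standardised effect is the same. For H1 (SD 11, n = 21 per group) with a quarter overlapping, the gap falls from 10 to 10 − 0.75 = 9.25 or 10 − 1.5 = 8.5 points. Power falls to 76% or 69%, from 82% by the same method (the plan states 80%).

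**6. Diet (illustration only).** No section gives usual fat intake. Assume 80 g/day at Visit 1, 9 kcal/g, and fat losses of 15% off and 6% on enzyme (from CFA 85% and 94%). If usual intake at Visit 2 is 70 or 60 g/day:
- No drug effect: stool energy falls by 10 × 0.15 × 9 = 13.5 or 20 × 0.15 × 9 = 27 kcal/day. The paired test (SD 56, n = 22) is then significant 19% or 58% of the time, instead of 5%.
- Planned drug effect: the spurious part is 10 × 0.06 × 9 = 5.4 or 20 × 0.06 × 9 = 10.8 kcal/day, against the planned 36.

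A usual intake of 80 g/day gives no bias; 90 or 100 g/day gives the same amounts in the opposite direction. A different assumption, that stool energy moves in proportion to intake, gives 250 × 5%, 10% or 15% = 12.5, 25 or 37.5 kcal/day and false rejection of 17%, 52% or 85%. The answer depends heavily on the assumption.

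**The case against.** On diet, Section 4.3 is silent rather than contrary. Section 5.2.2 names both visits, Section 4.2 calls them identical apart from listed items, and eligibility requires that subjects can eat a moderate-fat diet. A reader who starts from the method text would apply the same diet twice. The Day 5 return to usual diet is not peculiar to Visit 2 either: Table 3 shows it after the MBT in all three rows. This stands to the extent that nothing shows a decision to drop the diet. It does not remove the conflict. The Visit 2 list is otherwise complete day by day, Table 3 names a moderate-fat diet in no row, and a day list is the text most likely to be turned into subject instructions.

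On timing, the harmful bookings at +7 and +8 are ruled out by the Synopsis and by Sections 4.2, 5.2.2 and 9.4.2, and Section 3.1.3 is worded approximately. That is true, and it makes overlap less likely. But Section 3.1.3 still permits those days, and Creon36 is dispensed at Visit 1, so overlap is physically possible.

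On size, no document gives the diet shift or the share of subjects who would overlap, and taking the first Creon36 day at full effect overstates the loss. This stands: the figures are an illustration and an upper bound, not forecasts. The duration mismatch does not affect comparability; it is included because any single interval has to fit it.

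**Conclusion.** The concern holds. The day lists conflict with the method text on diet, two sections give Visit 2 windows that share only +12 to +14, the first stool day is stated two ways, and the longer window exceeds the four-week cap. These contradictions are certain from the text; the harm depends on which passage staff follow.

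- **Diet:** bias to H2, mainly in stool energy, of unknown size and direction. The MBT is unaffected and CFA% partly protected. H1 is not affected, because both Visit 1 lists carry the diet line.
- **Overlap:** dilution of H1 and H2 for CFA% and stool energy, only at +7 or +8. Paired power is 75% or 67% with a quarter of subjects affected, under the full-effect assumption; there is no effect from +9.

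It should be fixed, but it does not call the sample size or the MBT comparison into question.

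**What to change.** Reconcile the Synopsis (Study Phases and duration), Sections 3.1.3, 3.3.1, 4.2, 4.3, 5.2.2 (including Table 3) and 9.4.2 so that:

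- the diet instruction is stated consistently for both stool collections, in the day lists, Table 3 and the method text;
- the first stool day relative to the MBT is stated once;
- a single Visit 2 interval is given that agrees with the off-enzyme period around Visit 1 and with the stated participation length.

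What the diet and interval rules should be is for the sponsor to decide. The cost is protocol and subject-instruction wording, with no added visits, procedures or subjects.
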